3. STATISTICAL ANALYSIS

3.1. STATISTICAL PRINCIPLES

The statistical analyses for all the aims will be conducted as per this SAP and follow the statistical principles described below.

Participant flow diagram of this trial will be reported as specified by the Consolidated Standards of Reporting Trials (CONSORT) 2010 guidelines [4]. The flow diagram will display all stages of the trial such as screening, exclusions, enrollment, randomization, death, and study withdrawal.

Demographic information, clinical characteristics at baseline and study outcomes will be presented for each treatment group. Median and interquartile range (IQR) will be used for describing continuous variables, and frequency (%) will be used for describing categorical variables.

No hypothesis testing for the differences in baseline characteristics between the treatment groups will be conducted as recommended by the CONSORT 2010 guidelines for reporting parallel group randomized clinical trials [4-5].

Statistical significance level will be set at 5% for all outcomes. 95% confidence intervals will be reported with all effect estimates. No multiple comparison adjustments will be made for secondary and exploratory outcomes following the standard practice of analyzing multiple, prospective clinical trial outcomes [6-9]. No subgroup analyses will be conducted.

Missing data will be imputed, and the imputation process will be reported in detail. Since the percentage of missing data is anticipated to be lower than 5%, single imputation is planned to be used.

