1.2. RANDOMIZATION AND BLINDING

The trial aims to randomize 50 patients with delirium in the ICU in a 1:1 ratio to IV guanfacine or placebo. A computer-generated randomization scheme (with permuted block sizes) was created by the study's primary biostatistician and uploaded directly into REDCap's randomization module [1-2]. Investigators, patients, and clinicians will be blinded for the duration of the study until the database is locked.

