1.3. POWER ANALYSIS AND SAMPLE SIZE

Prior to beginning enrollment, our goal was to enroll and randomize 100 participants. We estimate that the participants in the placebo group will have 6.9±5.2 delirium/coma-free days (DCFDs) during the 14-day interventional study period based on the results from the recently completed Maximizing the Efficacy of Sedation and Reducing Neurological Dysfunction and Mortality in Septic Patients (MENDS2) study that used similar entry criteria [3]. Enrolling 100 patients would provide us at least 80% power to detect a 3 DCFDs

difference between the treatment groups over 14-day period for Aim 1. For Aim 2, we estimate that the participants in the placebo group will have 15.4±10.9 ventilator-free days (VFDs) and 13±10 ICU-free days (IFDs) based on the results from our MENDS2 study. Enrolling 100 patients would provide us at least 80% power to detect a 6 VFDs and 5.6 IFDs difference between the treatment groups over 28-day period.

Due to low enrollment and, given that this is a phase II proof-of-concept trial to guide safety and preliminary efficacy for future work, our final enrollment target was reduced from 100 to 50 with approval from the National Institute of Health and the Data and Safety Monitoring Board.

By analyzing 50 patients, we will have 80% power to detect a difference of 4.2 DCFDs over 14 days between the IV guanfacine and placebo groups. By analyzing 50 patients, we will have 80% power to detect a difference of 8.8 VFDs and 8.1 IFDs over 28 days between the IV guanfacine and placebo groups.

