2. OUTCOMES

2.1. PRIMARY OUTCOME

The primary outcome is delirium/coma-free days (number of days alive without delirium or coma) for 14 days starting on the day of randomization.

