3.3. ANALYSIS METHODS AND MODEL ASSUMPTIONS

All outcomes will be analyzed using regression models. Since this is a phase II proof-of-concept randomized controlled trial, unadjusted analyses will be the primary analyses, where the models will only have the treatment variable and will not be adjusted for any covariates.

Proportional odds logistic regression (POLR) will be used for modeling skewed continuous outcomes [10-11]. Proportional odds assumptions will be checked graphically using multiple cutoffs of the outcome, i.e., binary logistic regression models will be fitted using different cutoffs of the outcome, and the log odds ratios (estimated coefficients) will be plotted against cutoffs to check proportionality assumption [10]. Odds ratios along with 95% confidence intervals will be reported for POLR models.

Simple linear regression will be used for continuous outcomes that are normally distributed and satisfy the other assumptions. Assumptions will be checked graphically using residuals versus fitted values plots and quantile-quantile plots. Regression coefficients along with 95% confidence intervals will be reported for linear regression.

For 90-day mortality, Kaplan-Meier survival curve stratified by the treatment groups will be reported. Patients alive at 90-day will be censored at 90-day. Patients whose death information is unknown will be censored at their last known date alive.

Adjusted analyses will be conducted as sensitivity analyses. For adjusted analyses, all outcomes will be modeled using multivariable regression methods adjusting for the following covariates: age and severity of illness (measured by SOFA score) at randomization. If we have sufficient degrees of freedom in the model, interaction of age and treatment will be evaluated using an interaction term in the model. Otherwise, descriptive statistics will be generated by subgroups. For multivariable regression models, depending on the distribution of the variable, non-linear relationships between the outcome and the continuous covariates will be incorporated into the statistical models using restricted cubic splines with 3 knots when appropriate.

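### Planned single imputation makes the intervals slightly too narrow or dilutes the effect, depending on the unstated method; a simple multiple imputation including arm would cost little

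*Combined protocol and SAP*

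**What the plan says.** Section 3.1 covers missing data in two sentences. The first is a general commitment: "Missing data will be imputed, and the imputation process will be reported in detail". The second gives the method and its only justification: "Since the percentage of missing data is anticipated to be lower than 5%, single imputation is planned to be used". The section does not say which single-imputation method is meant, whether it uses treatment arm, or what the percentage is taken over.

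The primary outcome in section 2.1 is "delirium/coma-free days (number of days alive without delirium or coma) for 14 days starting on the day of randomization". Under section 3.3, "unadjusted analyses will be the primary analyses, where the models will only have the treatment variable and will not be adjusted for any covariates". That section also has the one other rule for unknown data, which serves 90-day mortality only: "Patients whose death information is unknown will be censored at their last known date alive". The sensitivity analyses in section 3.3 are covariate-adjusted models; none addresses missing outcomes. Incomplete follow-up is foreseen, because section 3.1 lists study withdrawal among the stages of the flow diagram.

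**The concern.** A filled value carries less information than an observed one, but after single imputation the model counts it in full. If the filled value comes from the patient's own arm, the standard error is too small and the test rejects too often. If it comes from both arms pooled, the two groups are pulled together and the estimated effect is diluted. The plan's wording allows either, and also allows carrying forward the patient's last status, which has almost no effect on the level.

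The affected results are the day-count outcomes: DCFDs, ventilator-free days (VFDs), ICU-free days and hospital-free days. Mortality has its own censoring rule, and missing age or SOFA would touch only the adjusted sensitivity models. What is at stake is the nominal 5% level and the coverage of the 95% intervals, by a small amount.

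**Working it through.** **Inputs.** 50 patients allocated 1:1, so 25 per arm (section 1.2); placebo DCFDs 6.9, SD 5.2, and a detectable difference of 4.2 (section 1.3); a 14-day window (section 2.1); a 5% level (section 3.1), taken as two-sided because the sidedness is not stated.

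**1. The plan's own figure.** The standard error is 5.2 × √(2/25) = 1.471, and 4.2 / 1.471 = 2.856. Normal-approximation power is Φ(2.856 − 1.96) = 81.5%. The t-test gives 79.9%, with a detectable difference of 4.21. The stated 80% is reproduced, so these inputs are a sound base.

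**2. What 5% could mean.** By patients, 2/50 = 4% and 3/50 = 6%. By patient-days, the total is 50 × 14 = 700. If 3 patients withdraw after day 2 to 7, each loses 9.5 days on average, and 3 × 9.5 / 700 = 4.1%, still below 5%.

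**3. Filling by a random draw from the same arm: hand check.** Suppose one patient is missing per arm. One of the 24 observed values is then used twice. The variance of the arm mean is σ²(23 + 2²)/25² = 1.08 × σ²/25. The expected sample variance is (25 − 1.08)/24 = 0.997 σ². True over reported variance is 1.08/0.997 = 1.084, so the standard error is too small by a factor √1.084 = 1.041. The effective critical value is 1.96/1.041 = 1.883, and the two-sided error is 6.0%.

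With 3 missing (2 in one arm, 1 in the other), the two-missing arm has an expected sum of squared weights of 23 + 4 + (2 + 2/23) = 29.09. Its multiplier is 29.09/25 = 1.163 and its sample variance is 0.993 σ². The ratio is (1.163 + 1.080)/(0.993 + 0.997) = 1.127, its root is 1.062, the critical value is 1.846, and the error is 6.5%. Neither the mean nor the SD enters, so the result carries over approximately to the other day-count outcomes.

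**4. Simulation, whole-patient outcome missing.** DCFDs on 0 to 14 with mean 6.9 and SD 5.2 (beta-binomial), missing at random, up to 60,000 null trials per setting. The test is the tie-corrected Wilcoxon, which is the score test of the treatment-only proportional odds model. Ranges are across repeated runs.

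| Type I error | 2 of 50 | 3 of 50 | 5 of 50 |
|---|---|---|---|
| Complete data | 5.0–5.1% | 4.9–5.1% | 5.0–5.1% |
| Single draw, same arm | 5.8–6.0% | 6.4–6.7% | 7.4–7.8% |
| Median of same arm | 6.4–6.6% | 7.3–7.5% | 9.3–9.8% |
| Single draw, arm ignored | 4.9–5.1% | 4.9–5.1% | 5.0% |
| Multiple imputation within arm | 5.0–5.2% | 5.1–5.2% | 5.1–5.3% |

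Multiple imputation used 20 data sets pooled by Rubin's rules. Its intervals were about 2%, 3% and 5% wider than those after single imputation.

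**5. Dilution when arm is ignored.** The expected difference is 4.2 × (1 − m/50): 4.03 for m = 2, 3.95 for m = 3 and 3.78 for m = 5. The loss with 2 missing is 4.2 × 2/50 = 0.17 days.

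**6. Partial follow-up.** Here delirium status follows a two-state daily model with the same mean and SD, and patients withdraw at random after day 2 to 7. For 2, 3 and 5 withdrawn, the type I error is 5.0%, 4.9% and 4.8% with complete data; 5.4%, 5.6% and 6.0% with a single draw of the remaining days from arm-specific transitions; 5.2%, 5.2% and 5.3% with multiple imputation from the same model; and 5.0%, 4.9% and 4.8% with last status carried forward. Multiple imputation widens intervals by 0.7%, 1.0% and 1.7%.

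**The case against.** The best defence is that the effect is close to nil where it is most likely to occur. The analysis set is limited to patients who received study drug, so part-way withdrawal is a more plausible route to a missing outcome than having no usable days. With 2 withdrawals, multiple imputation brings the error from 5.4% to 5.2%, a gain of 0.2 points against a simulation error of about 0.1. The 6.5% figure needs whole outcomes missing and an arm-median fill, which the plan does not name. With an arm-blind or carried-forward fill the level is not inflated. The trial is a phase II proof of concept, and the imputation process will be reported. All of this stands and sets the severity at low. It does not make single imputation the better choice, since the alternative costs little.

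Two stronger readings are tempting. A reader might infer that 5% is a threshold which a third missing patient would breach with no fallback. The text words it as an expectation supporting the chosen method, and 3 of 50 is 6% only when patients are counted; three withdrawals can be 4.1% of patient-days. The unstated denominator and fallback are therefore missing detail, not an error.

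A reader might also infer that multiple imputation removes a bias that single imputation has. The bias comparison available sets multiple imputation against complete-case analysis, so it does not test the planned method. A single draw from the same model has the same expected fill as repeated draws; the gain is in the standard error.

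**Conclusion.** The point holds as a low-severity, cheap improvement. Single imputation using arm understates uncertainty. With 2 of 50 patients missing, the excess type I error is about 1 to 1.5 percentage points for whole-patient outcomes and about 0.4 points for part-way withdrawal. With 3 whole outcomes missing the error is 6.5% to 7.5%. Single imputation ignoring arm keeps the level but takes about 0.2 days off a 4.2-day difference with 2 missing. Carrying forward the last status leaves the level unaffected.

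These sizes assume 25 per arm, the plan's mean and SD, a two-sided 5% test and the imputation methods shown, because the plan names none. The partial follow-up figures also depend on the assumed daily model. Missingness that depends on unobserved delirium status was not assessed. Nothing here puts the primary analysis in serious doubt.

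**What to change.** In section 3.1, replace single imputation with multiple imputation for DCFDs, VFDs, ICU-free days and hospital-free days, wherever the outcome cannot be derived from observed data. The imputation should include treatment arm and the patient's observed days, use about 20 data sets, fit the planned section 3.3 model in each, and pool by Rubin's rules. The model should stay simple, given about 25 patients per arm. Its exact form can be left to the trial statistician but must be fixed before unblinding. Used at any rate of missingness, this also removes the need to define a 5% threshold.

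Report complete-case results as a sensitivity analysis only, noting that they can be biased if withdrawal depends on delirium status. When withdrawals were confined to patients still delirious on their last observed day, complete-case analysis estimated a true 4.2-day difference as 4.1, 4.0 and 3.8 with 2, 3 and 5 withdrawn.

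The cost is modest programming and intervals about 1% to 3% wider with 2 or 3 patients missing. Sample size, outcomes and the main model are unchanged.

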3.2. ANALYSIS POPULATION

Analysis population will be based on the modified intent-to-treat (ITT) principle for all outcomes. The analysis cohort will include patients who were randomized and received study drug for all the primary, secondary and exploratory outcomes unless otherwise specified in this SAP.

3.3. ANALYSIS METHODS AND MODEL ASSUMPTIONS

All outcomes will be analyzed using regression models. Since this is a phase II proof-of-concept randomized controlled trial, unadjusted analyses will be the primary analyses, where the models will only have the treatment variable and will not be adjusted for any covariates.

Proportional odds logistic regression (POLR) will be used for modeling skewed continuous outcomes [10-11]. Proportional odds assumptions will be checked graphically using multiple cutoffs of the outcome, i.e., binary logistic regression models will be fitted using different cutoffs of the outcome, and the log odds ratios (estimated coefficients) will be plotted against cutoffs to check proportionality assumption [10]. Odds ratios along with 95% confidence intervals will be reported for POLR models.

Simple linear regression will be used for continuous outcomes that are normally distributed and satisfy the other assumptions. Assumptions will be checked graphically using residuals versus fitted values plots and quantile-quantile plots. Regression coefficients along with 95% confidence intervals will be reported for linear regression.

For 90-day mortality, Kaplan-Meier survival curve stratified by the treatment groups will be reported. Patients alive at 90-day will be censored at 90-day. Patients whose death information is unknown will be censored at their last known date alive.

Adjusted analyses will be conducted as sensitivity analyses. For adjusted analyses, all outcomes will be modeled using multivariable regression methods adjusting for the following covariates: age and severity of illness (measured by SOFA score) at randomization. If we have sufficient degrees of freedom in the model, interaction of age and treatment will be evaluated using an interaction term in the model. Otherwise, descriptive statistics will be generated by subgroups. For multivariable regression models, depending on the distribution of the variable, non-linear relationships between the outcome and the continuous covariates will be incorporated into the statistical models using restricted cubic splines with 3 knots when appropriate.

For the sensitivity analyses, redundancy analysis will be performed before modeling using an adjusted R^2 cutoff of 0.7 to evaluate for multicollinearity. Covariates that are highly correlated will be dropped from the model based on the rank order specified above. If the model is overfit, covariates will be reduced based on the rank order listed above.

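### The treatment-only primary model is valid, but fixing age and SOFA into the primary model before database lock is a cheap way to gain power if those covariates are prognostic

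*Combined protocol and SAP*

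**What the plan says.** Section 3.3 sets the primary analysis for all outcomes: "unadjusted analyses will be the primary analyses, where the models will only have the treatment variable and will not be adjusted for any covariates". The reason given is that this is a phase II proof-of-concept trial.

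The same section continues: "Adjusted analyses will be conducted as sensitivity analyses". The covariates are "age and severity of illness (measured by SOFA score) at randomization". The form of that adjusted model is left open. Section 3.3 allows three-knot splines where judged appropriate, an age-by-treatment interaction if degrees of freedom permit, and the dropping of covariates for collinearity or overfitting.

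The outcome model follows from the distribution. Skewed outcomes get proportional odds logistic regression (POLR); otherwise, "Simple linear regression will be used for continuous outcomes that are normally distributed and satisfy the other assumptions".

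Section 1.3 gives the planning figure after the target was cut from 100 to 50: "By analyzing 50 patients, we will have 80% power to detect a difference of 4.2 DCFDs over 14 days". Its placebo means and SDs come from the previous sedation trial, MENDS2; for ventilator-free days (VFDs) and ICU-free days (IFDs) they are "based on the results from our MENDS2 study". Section 3.2 limits the analysis to "patients who were randomized and received study drug", and section 3.1 adds that "95% confidence intervals will be reported with all effect estimates".

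**The concern.** Halving the target raised the 80%-power difference from 3 to 4.2 DCFDs out of 14, against an expected placebo mean of 6.9. The analysed cohort may be smaller than 50, because undosed patients are excluded. In a trial this small, prognostic baseline covariates are one of the few ways to gain precision without more patients. The SAP has already chosen two and needs no new data to use them, yet keeps them out of the primary model. The phase II label does not address efficiency, which matters more when N is small.

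At stake is the power of the primary comparison and, on the linear scale, the width of its interval. Bias is not at stake.

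**Working it through.** **Inputs.** Section 1.3: SD 5.2 for DCFDs, 10.9 for VFDs and 10 for IFDs; N = 50; difference 4.2 DCFDs. Section 1.2: 1:1 allocation, taken as 25 per arm. Section 3.1: 5% significance level, taken as two-sided. Section 3.3: two covariates, so p = 2 if both are linear. R² (within-arm outcome variance explained by age and SOFA) is in neither section; 0 to 0.30 is assumed.

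**Step 1: the plan's own figure.** Noncentrality = 4.2 / (5.2 × √(4/50)) = 4.2 / 1.471 = 2.856. With 48 degrees of freedom the critical value is 2.011 and power is 79.9%. The 80%-power difference is 4.21 days. The VFD and IFD figures for 50 patients also reproduce (79.9% at 8.8 days, 80.1% at 8.1 days).

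**Step 2: add two fixed linear terms.** Divide the noncentrality by √[(1 − R²) × (1 + p/(N − p − 3))] = √[(1 − R²) × 47/45] and use 46 degrees of freedom (critical value 2.013). Two examples:

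- R² = 0: 2.856 / 1.022 = 2.794, power 78.1%.
- R² = 0.20: 2.856 / 0.914 = 3.124, power 86.4%.

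The table averages over chance covariate imbalance, which moves the power figures by no more than about 0.1 point.

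| R² (assumed) | Power at 4.2 DCFDs | Change from 79.9% (points) | 80%-power difference: DCFDs | VFDs | IFDs |
|---|---|---|---|---|---|
| Unadjusted | 79.9% | – | 4.21 | 8.8 | 8.1 |
| 0 | 78.1% | -1.8 | 4.30 | 9.0 | 8.3 |
| 0.05 | 80.2% | +0.3 | 4.19 | 8.8 | 8.1 |
| 0.10 | 82.2% | +2.3 | 4.08 | 8.6 | 7.8 |
| 0.20 | 86.4% | +6.5 | 3.85 | 8.1 | 7.4 |
| 0.30 | 90.5% | +10.6 | 3.60 | 7.5 | 6.9 |

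**Step 3: break-even.** The variance factor alone gives 1 − 45/47 = 0.0426. Allowing for the two lost degrees of freedom gives 0.0443, or 0.0439 averaged over imbalance: about 0.044. With three-knot splines on both covariates (p = 4) it is about 0.088. If 46 are analysed (assumed), unadjusted power is 76.4%, adjusted power is 74.4, 76.5, 78.7, 83.2 or 87.8% at the same R² values, and break-even is about 0.048.

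**Step 4: POLR, by simulation.** Assumptions: placebo DCFDs beta-binomial on 0-14 (mean 6.9, SD 5.2), two normal covariates with equal effects, proportional odds holding conditionally, permuted blocks of 4.

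- *Power at 4.2 DCFDs, likelihood-ratio test.* Unadjusted power is about 88-89%. Adjusting changes it by about -1, +3, +5 or +8 points at latent R² 0, 0.10, 0.20 or 0.30. Read these to about a point.
- *Type I error, 50 analysed.* Adjusted likelihood-ratio 6.1-6.3% (unadjusted 5.3-5.8%), adjusted Wald 5.8-6.1%, adjusted permutation 4.6-5.1%. With 46 analysed: adjusted likelihood-ratio 5.8-6.8%, permutation 4.4-5.1%.
- *Interval.* The adjusted 95% Wald interval covers 93.6-94.7%.
- *Linear branch on the same null data.* The adjusted t-test runs at 4.6-5.4%, so it needs no correction.

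A second POLR simulation drew a normal latent outcome with a 4.2-day shift, rounded and cut off at 0 and 14. Likelihood-ratio power, unadjusted against adjusted, was 76.7 vs 76.6% at R² 0, 78.6 vs 79.5% at 0.044, 78.3 vs 81.9% at 0.10 and 78.9 vs 85.6% at 0.20. The baseline depends on the assumed outcome shape; the direction and rough size of the change do not.

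Power of the permutation test was simulated only at a smaller difference, 3.6 DCFDs. There adjusting changes it by -2.6, +0.7, +2.9, +7.9 or +12.9 points at latent R² 0, 0.05, 0.10, 0.20 or 0.30, from an unadjusted 71-73%. Those are not the gains at the SAP's 4.2 days.

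**The case against.** The plan is coherent as it stands. The unadjusted model is prespecified, matches the basis of the power statement, and is accompanied by the adjusted analysis, so the question is only which of two planned models is called primary. That stands, and is why this is a suggested improvement and not a defect.

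The benefit also rests on an R² that the documents do not supply. At 0.05 the linear gain is 0.3 points and at 0.10 it is 2.3; worthwhile gains need about 0.20 or more. That stands too. So does the point that the simulations assume linear covariate effects and conditional proportional odds, with no misspecified case tested. Hospital-free days have no calculation at all, since section 1.3 gives no SD for them.

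Four stronger readings are tempting, and the documents support none of them:

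- *Omitting age and SOFA biases the result, or chance imbalance invalidates it.* Randomization makes the treatment-only comparison valid.
- *The power claim for 50 patients is wrong.* It reproduces.
- *Adjustment is bound to raise power.* Below the break-even R² it lowers it.
- *The existing sensitivity model could simply be promoted.* Its splines, interaction and covariate removal are open choices, unsuited to a primary analysis. The 0.044 threshold does not describe that model, nor does it apply to POLR. In the second simulation the nominal POLR break-even was about 0 to 0.02, partly because the adjusted test is liberal.

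**Conclusion.** A cheap, optional improvement. Over the assumed R² range of 0 to 0.30, the linear basis shows a loss of 1.8 points of power at worst and a gain of 10.6 at best at 4.2 DCFDs with 50 analysed. Under POLR with the assumed beta-binomial outcome the range is about -1 to +8 points from a baseline of 88-89%, slightly flattered by the liberal adjusted test. The downside is small and bounded and the upside is larger, but where the trial lies in that range cannot be settled from the documents.

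The case holds only if the covariate terms are fixed in advance, only before database lock and unblinding, and, under POLR, only with a p-value that keeps its size. The documents do not show whether lock has passed.

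**What to change.** If the database is not locked and the trial is still blinded, replace the primary-model statement in section 3.3 with wording such as:

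> The primary model for DCFDs, and likewise for VFDs, IFDs and hospital-free days, contains treatment, age and SOFA score at randomization as fixed linear terms, with no splines, interaction or covariate removal. It is POLR or linear regression by the existing rule in this section. Under linear regression, the estimate, 95% confidence interval and p-value come from the model. Under POLR, the model supplies the odds ratio, conditional on age and SOFA, and its 95% confidence interval; the primary p-value comes from a permutation test that reassigns treatment labels within the modified ITT cohort with arm sizes held fixed. If interval and p-value disagree about significance, the permutation p-value decides. The treatment-only model is the sensitivity analysis. The spline, interaction, redundancy and overfit rules apply only to further sensitivity models. The 90-day mortality analysis is unchanged.

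In section 1.3, label the power figures as referring to the treatment-only comparison. If age and SOFA were recorded in MENDS2 (the documents do not say), R² could be estimated there to replace the assumed range, but the SAP should name one primary model outright and not leave the choice conditional.

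**Cost.** SAP wording, one label and a short permutation routine; no new data. The trial gives up 2 degrees of freedom, about 2 points of power on the linear basis if the covariates are not prognostic, and, under POLR, a marginal odds ratio in favour of a conditional one whose nominal 95% interval covers about 94%. If lock or unblinding has passed, leave the primary model as it is.
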